3.2 Study Population

We propose to enroll 368 HIV-positive individuals for the purposes of this study. Approximately 48 participants will be recruited for focus group discussions (with the goal of 8 per group), 12-20 participants will be recruited to conduct usability testing of the *YT* intervention, and 300 participants (n=150 *YT* and n=150 control) will be recruited to participate in the *YT* RCT. An enrollment target of 50% for illicit drug use and/or problematic alcohol use in the past 6 months is set for each SRV. Participants who are pregnant at the time of screening or who become pregnant during the study period will not be excluded from the study.

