YT	YouTHrive

STUDY ABSTRACT

DESIGN:	
YouTHrive (YT) is a two-arm randomized controlled trial (RCT) to test the efficacy of an adapted version of the Thrive With Me intervention for youth living with HIV (YLWH).

DURATION:	YLWH are enrolled for 5 months.
SAMPLE SIZE:	Total study sample is 368 of which the following will be enrolled for each aim: 1) 48 participants for focus groups to inform intervention adaption; 2) 12-20 participants for usability testing to finalize intervention components; 3) 300 participants for a randomized controlled trial of YT, with participants randomized to either YT (n=150) or control (n=150).
POPULATION:	Participants for all aims of the study will include YLWH inclusive of all genders and all races/ethnicities. Focus group participants will be recruited from SRVs in Bronx, Chicago, and Houston. Usability participants will be recruited from SRVs in Bronx, Chicago, Houston, Philadelphia, Tampa, and Atlanta. RCT participants will be recruited from SRVs in Bronx, Chicago, Houston, Philadelphia, Tampa, Atlanta, Raleigh/Durham/Chapel Hill and Charlotte area. Usability participants must have had a detectable VL in the past 12 months. RCT participants will be required to meet eligibility criteria.
STRATIFICATION:	Focus group discussions will be stratified by age (50% 15-19 yo; 50% 20-24 yo). We will stratify by SRV (i.e., city) site for the RCT.
DATA COLLECTION:	Focus group discussions will be conducted in-person, digitally recorded, and professionally transcribed. There will be three data collection (screening, baseline, and 5-month) time points for the RCT. Visits are conducted in-person at the SRV or remotely. Surveys will be completed using online survey tools (Alchemer and Qualtrics). VL measure collection will occur in-person at the participant's SRV or remotely. Urine screen will happen at in-person visits only. Process data of participant activity on YT and control interventions will include log-in activity, tasks completed on the website, and number of written posts.

OBJECTIVES:

- 1) In a 2-arm RCT (n=300), assess the efficacy of YouTHrive (YT) to sustain suppressed viral load (VL) among YLWH, compared to an HIV information-only control condition.
- 2) Assess whether YT is more beneficial for substance-using than non-substance-using YLWH.

INTRODUCTION

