The “Thrive with Me” (*TWM*) intervention leverages enhanced peer-to-peer interaction, ART adherence reminders and self-monitoring, and ART and HIV informational content²¹ to improve ART adherence. In a pilot study of 123 adult MSM (average age = 43 years), those randomized to the *TWM* intervention showed improvements across all ART adherence outcomes compared to control participants, with greatest benefits for current drug-using MSM. Currently, our research team is funded to conduct an efficacy trial of an extended (5-month intervention period) and enhanced (tailored informational content; multi-dimensional self-monitoring; and gamification components, such as leveling and badges) version of the *TWM* intervention for adult MSM. Given youth’s broad acceptance and adoption of many of the components of the *TWM* intervention, and the critical need for novel and scalable ART adherence interventions for this population, the next logical step is to adapt the *TWM* intervention for YLWH.

As part of the UNC/Emory Center for Innovative Technology (iTech), we propose to test the efficacy of an adapted version of the *TWM* intervention, called YouT^Hrive (YT), for YLWH. In this 4-year study, 300 YLWH between the ages of 15-24 with detectable viral load (VL) will be randomized to the YT or an HIV information-only control intervention for a 5-month period. A target of 50% of YLWH participants with self-reported alcohol and/or illicit drug use will be enrolled. The primary endpoint is VL post-intervention.

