2.3 Study Hypotheses/Research Questions

- *H1: A higher proportion of participants in the YT intervention arm than in the information-only control arm will have undetectable VL at the 5-month follow-up time point.*
- *H2: Among YLWH in the YT intervention arm, a higher proportion of substance-using YLWH will demonstrate VL suppression at the 5-month follow-up time point compared to non-substance-using YLWH.*

STUDY DESIGN

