YLWH will be recruited from 8 SRVs (Bronx, Houston, Chicago, Philadelphia, Tampa, Atlanta, Raleigh/Durham/Chapel Hill, and Charlotte). Persons interested in the study will be screened to determine if they meet the eligibility criteria. Prospective participants can screen remotely or in person, and can be recruited within the SRV clinic or in the community, as long as they meet inclusion criteria. YLWH who meet all inclusion criteria will be invited for either an in-person or virtual enrollment visit. Screening and enrollment may also happen during one visit, when possible.

At the enrollment visit, participants will complete an in-office or online baseline CASI, complete a viral load test if one was not performed in the past 60 days, a urine screen for recent drug use, and will be randomized at survey outset to either intervention or control. The randomization sequence will be stratified by city and use random permuted blocks of size 2 and 4. YLWH assigned to the *YT* intervention will be shown example webpages of the intervention, will be given basic training on how to navigate the intervention, and will be given the opportunity to ask questions they have about the website. Control condition assigned participants will be shown example webpages they will receive during the intervention period.

The intervention period lasts five months. During this time, intervention participants will have continuous access to the *YT* website (mobile enhanced and available on all devices with internet connection). Participants in the control condition will receive an email with HIV-related information once per week.

Follow-up assessments will be conducted at the 5-month (i.e., immediate post-intervention; follow-up 1 in the clinical setting or online via a teleconferencing platform such as VSee or Zoom) time point. The 5-month follow-up visit will include an in-office or online administered CASI, a blood draw or self-administered finger prick to test for detectable viral load, and a urine screen for drug use. At the 5-month follow-up visit, up to 20 intervention participants will be offered additional compensation (as specified in each SRV's informed assent/consent form) to take part in an additional semi-structured interview with SRV staff or via Zoom with a member of the study team.

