During the enrollment visit for Aims 2 and 3, SRV staff will confirm the participants' eligibility. YLWH who are eligible for the study will be guided through an informed consent process by research staff. Next, participants completing will complete a computer-assisted baseline survey, created by AC staff and hosted on Alchemer, a secure, HIPAA-compliant platform. During the RCT, participants will then be randomized 1:1 to YT intervention or control group, based on a randomization sequence developed by the AC lead statistician and loaded into DFExplore via SAS. The randomization sequence will be stratified by city and use random permuted blocks of size 2 and 4. The time between screening to enrollment must not exceed 60 days. If more than 60 days lapses between the screening and enrollment visit, then a person must be re-screened (see section 4.5). Participants will be considered enrolled upon signing the enrollment RCT consent form, completing the CASI, completing either an in-person or virtual enrollment visit, and being randomized to YT intervention or control.

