10.3.4 Secondary Analyses for RCT of YouTHrive

As a secondary aim, we will investigate whether there is greater benefit from the YT intervention for substance-using participants compared with nonsubstance-using participants. We will use the same modeling approach described above to address this aim. First, we will examine the association between the intervention and viral detection separately among those who did and did not self-report current (since the last visit) substance use (i.e., yes/no for problematic alcohol use and/or illicit drug use). Second, to formally test whether there is an interaction between intervention arm and substance use, the models described above will be refit including an interaction term between substance use and intervention arm. Interactions will be evaluated on the additive scale. We will carefully examine the distribution of potential confounders of the substance use and VL association and adjust for them as necessary. As mentioned previously, we will adjust for covariates where appropriate.

The models described use logistic regression to model the outcomes. We will use estimates from these models to report prevalence differences and ratios. However, alternative (log-linear and Poisson) models may be explored to allow easy interpretation of parameters in the presence of common outcomes. In the event of loss-to-follow-up among study participants, we will perform sensitivity analyses of an alternative outcome. We will define an additional outcome where a failure is defined as either detectable VL or loss-to-follow-up. The analyses described above will be repeated with this alternative outcome. All of the models mentioned above can be modified to accommodate missing values in the outcome or covariates over time without dropping participants. Although attempts will be made to limit missing data, in the event that this occurs, we will carefully examine patterns of missingness. Multiple imputation will be implemented, as needed, to deal with missing covariate data.

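### The 50% substance-use enrolment target (past 6 months) and the moderator in 10.3.4 (use since an unnamed last visit) cover different periods, and the moderator may be measured after randomization

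*Combined protocol and SAP*

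**What the plan says.** - **Enrolment target, 3.2 Study Population:** "An enrollment target of 50% for illicit drug use and/or problematic alcohol use in the past 6 months is set for each SRV".
- **Moderator, 10.3.4:** the intervention effect is examined separately in those who did and did not "self-report current (since the last visit) substance use (i.e., yes/no for problematic alcohol use and/or illicit drug use". For the formal test, "the models described above will be refit including an interaction term between substance use and intervention arm". The section does not say at which visit the item is taken.
- **Secondary hypothesis, 2.3 (H2):** within the YouTHrive arm, "a higher proportion of substance-using YLWH will demonstrate VL suppression at the 5-month follow-up time point compared to non-substance-using YLWH". No window is given for being substance-using.
- **Background, 1.1:** "A target of 50% of YLWH participants with self-reported alcohol and/or illicit drug use will be enrolled". This wording has no window and does not limit alcohol use to problematic use.
- **Visits:** the Study Abstract says "There will be three data collection (screening, baseline, and 5-month) time points for the RCT". Section 5.1 says "The time between screening to enrollment must not exceed 60 days", and 3.1 adds: "Screening and enrollment may also happen during one visit, when possible". Section 6.3 allows the 5-month assessment from 30 days before to 60 days after its ideal date.

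**The concern.** Moderation by substance use is the plan's only secondary objective (2.2). The 50% target is the only enrolment provision that bears on it: randomization is stratified by city alone (3.3.3), and the power section (10.2.3) gives nothing for the interaction. If the variable that sites count toward the target is not the variable analysed, the balance obtained at enrolment need not carry over to the analysis.

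The timing matters more than the length of the window. A moderator recorded at the end of follow-up is itself a possible outcome of treatment. Comparing arms within strata of such a variable no longer compares randomized groups, and an arm-by-use interaction could then reflect who changed their use rather than who benefited.

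**Working it through.** **1. Is there a figure to reproduce?** Not for this analysis. Section 10.2.3 covers self-reported adherence, depression and social support only. Its adherence figure does reproduce: (1.960 + 0.842) × 43 × √(2/120) = 15.55, against the stated 15.6 points. It has no bearing on the interaction.

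**2. The windows side by side**

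| Use of the variable | Period covered |
|---|---|
| Target, 3.2 | the past 6 months, as counted for enrolment |
| Moderator taken at 5 months | enrolment to the 5-month visit: 5 months − 30 days to 5 months + 60 days, about 4 to 7 months, all after randomization |
| Moderator taken at baseline, screening counted as the last visit | 0 to 60 days before enrolment |

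The 5-month reading has no overlap with the target window. The baseline reading covers at most about a third of it (60 of roughly 180 days). Neither reading matches. Sections 3.2 and 10.3.4 do agree on substance type; they differ in window. Section 1.1 differs in the alcohol wording and gives no window.

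**3. Further consequences of the 5-month reading.** The value would be unknown for anyone lost to follow-up. Section 10.3.4 repeats its analyses with loss to follow-up counted as failure, so these participants would have an outcome but no subgroup. At the plan's follow-up of about 85%, that is 300 × 0.15 = 45 of 300. If all 300 enrol and the 240 used for power are followed, it is 300 − 240 = 60.

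**4. Illustration of dilution (assumed rates).** The documents give no reclassification rate. Let 50% be users by the target definition, *a* the share of those users analysed as non-users, and *b* the share of non-users analysed as users.

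- Share classed as users: u = 0.5(1 − a) + 0.5b
- PPV = 0.5(1 − a)/u; NPV = 0.5(1 − b)/(1 − u)
- Share of the additive interaction retained = PPV + NPV − 1

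For a = 40%, b = 0: u = 0.30, which is 72 of 240; PPV = 1; NPV = 0.5/0.7 = 0.714; retained 71%.

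| a | b | Classed as users, of 240 | PPV | NPV | Retained |
|---|---|---|---|---|---|
| 0 | 0 | 120 | 1.000 | 1.000 | 100% |
| 10% | 0 | 108 | 1.000 | 0.909 | 91% |
| 20% | 0 | 96 | 1.000 | 0.833 | 83% |
| 40% | 0 | 72 | 1.000 | 0.714 | 71% |
| 20% | 10% | 108 | 0.889 | 0.818 | 71% |
| 20% | 20% | 120 | 0.800 | 0.800 | 60% |
| 40% | 20% | 96 | 0.750 | 0.667 | 42% |

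The table assumes that target-defined status is the true moderator and that reclassification is unrelated to arm and outcome. On the 5-month reading the second assumption is the one in doubt, so the error could go in either direction and the table does not bound it.

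**The case against.** Several points on the other side are sound.

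- **Purpose of the target.** A reader might infer that the 50% target exists to give objective 2.2 two groups of equal size. The documents do not say so. Section 3.2 gives no reason, and a recruitment target may be broader than an analysis variable without being wrong. What stands is that nothing links the two, although both describe the same attribute.
- **The zero-day window.** A reader might infer that with same-day screening and enrolment nobody could be classed as a user. That requires the item to be taken at baseline and screening to count as a visit. Screening is an online survey (4.5), and 8.1 names enrolment and 5 months as the time points. The 5-month reading is more natural, and it brings the post-randomization problem with it.
- **Which window is the true moderator.** Section 1.1 reports the greatest pilot benefit in current drug users. If current use is what modifies the effect, classifying on it dilutes nothing, and a 6-month variable would add recent quitters to the user group. This stands as a caution against firm statements about attenuation. It does not justify a moderator measured after randomization.
- **Loss of power.** With 240 analysed, 50% undetectable in each cell, a true interaction of 30 points and one-way reclassification, power would fall from 64% to 33% if only 60% of target users were classed as users. All of these inputs except the 240 are assumed, so this is not an estimate of what the trial will lose.
- **Section 1.1.** A reader might infer that non-problem drinkers will fill the user half. Section 1.1 is background, and it also describes participants as having detectable viral load, which the RCT criteria in 4.1 do not require. Section 3.2 is the specific text.
- **Missing values.** Section 10.3.4 allows multiple imputation of missing covariates. That could fill in the moderator, but not make it a pre-randomization variable. The Schedule of Evaluations is not visible and might settle the timing; the analysis section should still state it.

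**Conclusion.** The mismatch is real. On either reading of 10.3.4, someone counted toward the 3.2 target can be analysed as a non-user, and the reverse. The more serious consequence comes with the more natural reading: the moderator is then open to influence by the intervention and absent for those lost to follow-up. The size of the effect on the secondary objective cannot be computed from the documents. The 42% to 91% retained is an illustration over assumed rates. The primary comparison of arms is not affected.

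**What to change.** In 10.3.4, replace the since-last-visit definition with self-reported illicit drug use and/or problematic alcohol use in the 6 months before enrolment, measured before randomization. Use that one variable for the 3.2 target at each SRV, for H2 and for the arm-by-substance-use interaction. Keep use since the last visit as a labelled exploratory variable, with its visit named. Conform 1.1 to the 3.2 wording.

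The requirement to measure before randomization needs one further step. Sections 3.1 and 3.3.3 randomize at the outset of the survey, while 5.1 and 5.3 randomize after it. Reconcile these, or take the item from the screening survey.

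The cost is wording. Monitoring the 3.2 target already requires the 6-month information. The downside is small: a 6-month window counts some people who stopped recently as users. If the team prefers a shorter window before randomization because of the pilot, the 3.2 target should be changed to the same window.

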3.3 Study Randomization, Stratification, or Description of Non-Random Assignment Procedures

3.3.1 Focus Groups

Focus groups will be stratified by age such that 2 focus groups (1 consisting of youth 15-19 year olds and 1 consisting of young adults 20-24 years old) will be conducted at each of the 3 SRVs. Study staff at each SRV will oversee that approximately 8 participants (with a minimum of 5) are recruited for each of the 2 focus groups conducted at that site. SRV study staff will have at least weekly check-ins with the AC lead and the *YT* protocol chair to provide updates about recruitment successes and challenges, and to brainstorm recruitment strategies that may be used should recruitment goals not be met.

3.3.2 Usability Testing

Usability testing participants will be recruited from 6 SRVs (Bronx, Chicago, Houston, Philadelphia, Tampa, and Atlanta) without stratification or random assignment. However, participant demographics for this aim should be closely monitored to ensure that diversity in ages, genders, and race/ethnicity is achieved at each site. Management Core will work with sites to recruit a diverse sample for usability testing. Each SRV will recruit two participants for

usability testing. One participant will be from the younger age group (15-19) and one from the older age group (20-24). SRV recruitment staff will be asked to recruit one male and one female at each site. In addition, across all SRV sites, we will recruit at least one perinatally infected female and at least one perinatally infected male to ensure that YouTHrive is relevant for youth infected through different transmission routes.

3.3.3 RCT

At outset of the survey, participants will be randomized 1:1 to YT intervention or control group, based on a randomization sequence developed by the AC lead statistician and loaded into DFexplore via SAS. The randomization sequence will be stratified by city and use random permuted blocks of size 2 and 4.

SELECTION AND ENROLLMENT OF STUDY PARTICIPANTS

4.1 Inclusion Criteria

Inclusion Criteria for Aim 2 Usability Testing

- 15-24 years of age at the enrollment visit
- HIV-positive status (medical chart-verified)
- In HIV clinical care in the Chicago, Houston, Bronx (NYC), Philadelphia, Atlanta, or Tampa area
- Currently prescribed ART (medical chart verified)
- Medical chart-verified detectable VL (above the lower limit of detection for the clinical assay) within 52 weeks of enrollment date and an ART prescription for at least 90 days prior to this VL test date
- English-speaking (since the intervention will be in English)
- Internet and SMS messaging access for the usability testing period (approximately two weeks)
- Available to meet with SRV staff in person for the first research appointment
- Availability to meet with UMN research staff for a remote (i.e., telephone or video-conference) feedback interview

Inclusion Criteria for Aim 3 Randomized Control Trial

- 15-24 years of age at the enrollment visit;
- HIV-positive status;
- Residing in Chicago, Houston, NYC, Philadelphia, Atlanta, Tampa, Raleigh/Durham/Chapel Hill, or Charlotte areas and available to meet with SRV staff for visits at baseline and 5-month follow-up assessment. Participants who are unable to attend in-person session will be given the option to complete assessments online;
- English-speaking (since the intervention will be in English);
- Anticipated continuous internet access and SMS messaging for the intervention period (approximately 5 months);
- Not enrolled in another ART adherence intervention research study at the time of screening;
- Has or is willing to create an e-mail address to use during the study period;
- Did not attend an iTech YAB (Youth Advisory Board)/YAC (Youth Advisory Council) meeting where the YouTHrive study was presented or YouTHrive study materials were discussed;

4.2 Exclusion Criteria

Exclusion Criteria for Aim 2 Usability Testing

- Aged younger than 15 years or older than 24 years
- HIV-negative
- Is not in HIV care in the Chicago, Houston, Bronx (NYC), Philadelphia, Atlanta, or Tampa area
- Not currently on ART medication (does not have an active ART prescription by a health provider)
- Does not have medical chart-verified detectable VL (above the lower limit of detection for the clinical assay) within 52 weeks of enrollment date and an ART prescription for at least 90 days prior to this VL test date
- Non-English speaking (since the intervention will be in English)
- Anticipate not having access to the internet or SMS messaging during the usability period (approximately two weeks)
- Not available to meet with SRV staff in person for first research appointment
- Not available to meet with UMN research staff for a remote (i.e., telephone or video-conference) feedback interview

Exclusion Criteria for Aim 3 Randomized Control Trial

- Aged younger than 15 years or older than 24 years
- HIV-negative
- Does not reside in Chicago, Houston, NYC, Philadelphia, Atlanta, Tampa, Raleigh/Durham/Chapel Hill, or Charlotte areas or is not available to meet with SRV staff for visits at baseline, and 5-month and follow-up assessment
- Non-English speaking (since the intervention will be in English)
- Anticipate not having access to the internet or SMS messaging for the intervention period (approximately 5 months)
- Enrolled in another ART adherence intervention research study at the time of screening
- Planning to move out of study area during the study period and unwilling to participate in virtual visits
- Unwilling or unable to comply with protocol requirements
- Participated in Aim 2 of the study (Aim 1 participants may be included if they meet other criteria)
- Does not have or is not willing to create an e-mail address
- Attended an iTech YAB (Youth Advisory Board)/YAC (Youth Advisory Council) meeting where the YouTDrive study was presented or YouTDrive study materials were discussed

All genders may participate in the study. Women who are pregnant at study onset or become pregnant during the study period are eligible and can be included as participants.

